OFFICIAL TITLE:

*THE EFFECTS OF PROBIOTICS ON
METABOLIC BIOMARKERS,
INFLAMMATION, AND THE
ANTIOXIDANT SYSTEM IN PATIENTS
WITH TYPE 2 DIABETES MELLITUS*

Date: 17.04.2018

Statistical Analysis Plan (SAP)

Statistical analysis was performed using SPSS 25.0 statistical package program. Data from all patients who completed the study were included in the statistical analysis. For descriptive findings, categorical variables were presented as numbers and percentages, and continuous variables were presented as mean, standard deviation, minimum value and maximum value. Kolmogorov-Smirnov normality tests were used to determine whether the data showed normal distribution. Pearson chi-square test was used to analyse categorical variables. Parametric tests (t test in independent groups, t test in dependent groups) were used in the analysis of normally distributed data, and non-parametric tests (Mann-Whitney U test, Wilcoxon Signed Rank Test) were used in the analysis of non-normally distributed data. Statistical significance level was accepted as $p<0.05$.

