Regulation of gut microbiota through dietary interventions (e.g., probiotic intake) may be beneficial in reducing inflammation [hs-CRP and Ceruloplasmin (Cp)] and oxidative stress [Glutathione (GSH) and Malondialdehyde (MDA)], as well as regulating glucose and lipid metabolism in T2DM. The aim of this study was to investigate the effects of probiotics on glucose and lipid metabolism, inflammation and antioxidant system in patients with T2DM.

Methods

Trial design

This was a single center, prospective controlled study conducted at the Internal Medicine Outpatient Clinic of Ege University Faculty of Medicine between July 2020 and June 2023. The study included a screening visit, a baseline visit (D0) and one follow-up visit during a 60-days supplementation period. The primary outcomes of the study were defined as the effects of the intervention on inflammatory markers, specifically focusing on a significant decrease in hsCRP and Cp levels, and oxidative stress markers, including a significant reduction in MDA levels and a significant increase in reduced GSH levels. Secondary outcomes included assessing the metabolic and lipid profile changes, which specifically targeted a significant decrease in Fasting Blood Glucose (FBG), Postprandial Blood Glucose (PPBG), and Glycated Hemoglobin (HbA1c), alongside a reduction in LDL-C and Triglyceride (TG) levels, and an increase in High-Density Lipoprotein Cholesterol (HDL-C) levels.

Trial participants

Power analysis was performed and the sample size was calculated as 79 with a statistical power of 80% and an effect size of 0.35. Since two groups were to be studied, 80 patients were planned to participate in the study to equalize the number of participants.

This study included adults aged 35-65 years who were diagnosed with T2DM according to American Diabetes Association guidelines, who volunteered to participate in this study. Exclusion criteria were as follows: Use of any systemic antibiotics, multivitamins, minerals, herbal medicines, prebiotic, probiotic and postbiotic supplements in the last 3-6 months, any inflammatory bowel disease, severe renal dysfunction or hepatic dysfunction, immunodeficiency diseases, acute infection, rheumatoid arthritis, cancer history, history of alcohol abuse or drug dependence, pregnant or lactating women. Dietary habits, physical activity, and glucose-lowering therapy of the participants were not intervened during the study.

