Participants were allocated sequentially according to order of presentation (alternate allocation). According to the order of presentation to the outpatient clinic, the first patient who met the inclusion criteria was included in the probiotic group and the second patient who presented to the outpatient clinic was included in the control group. Patients in the intervention group were given a probiotic supplement containing *Lactobacillus acidophilus*, *Lactobacillus rhamnosus*, *Bifidobacterium lactis* and *Lactobacillus paracasei*, each containing 1.25 billion live microorganisms, without vitamins and minerals, twice a day in addition to their current treatment for 12 weeks (Probiotic group). Patients in the control group were not given any

additional treatment and were allowed to continue their antidiabetic treatment for 12 weeks (Control group). Participants taking probiotics were instructed to discontinue probiotic intake if they experienced any serious adverse events requiring intervention. The probiotic product was supplied without placebo equivalent, and due to COVID-19-related supply limitations no identical-appearing placebo powder could be obtained. Sociodemographic data and medical data were recorded for all participants.

Anthropometric Measurements

Body weight, height, waist (WC) and hip circumferences (HC) were collected following the standardized procedures recommended in the World Health Organization Expert Committee Guidelines for physical examination at baseline and after 12 weeks [17]. Body mass index (BMI) (kg/m^2) and waist-to-hip ratio (WHR) (WC/HC) were calculated.

A Food Frequency Questionnaire (FFQ)

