The EAT-26 was developed for Garner et al.[24]. The test consists of 26 items, and the total score is between 0-53. A score of 20 and above is defined as “abnormal eating behavior” and a score less than 20 is defined as “normal eating behavior”. The Turkish validity and reliability study was conducted by Erguney-Okumus and Sertel-Berk [25].

Biochemical measurements

Fasting blood samples were collected from the participants at baseline and week 12, following overnight fasting and after 2 hours of satiety. FBG, PPBG, HbA1c, Total-C, LDL-C, HDL-C, TG and hs-CRP were measured using an autoanalyzer. Serum MDA levels were determined by the thiobarbituric acid method [26], GSH levels by enzymatic recycling method [27] and Cp levels by colorimetric method [27] using a microplate reader.

References

4. Choi SH, Chae A, Miller E, Messig M, Ntanios F, DeMaria AN, et al. Relationship Between Biomarkers of Oxidized Low-Density Lipoprotein, Statin Therapy, Quantitative Coronary

Angiography, and Atheroma Volume. *J Am Coll Cardiol.* 2008;52:24–32. <https://doi.org/10.1016/j.jacc.2008.02.066>.

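### The SAP analyses only patients who completed the study, without saying that sampled patients who stopped the probiotic stay in their group or testing the effect of missing follow-up (minor)

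*SAP*

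**What the plan says.** The SAP is a single section. On the analysis population it says only that "Data from all patients who completed the study were included in the statistical analysis". It then lists independent-group and paired tests, parametric or non-parametric, and a 5% significance level. Neither document defines completion, gives a method for missing values or plans a sensitivity analysis.

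Four statements in the protocol's Methods bear on this:

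- **Control arm (Trial participants).** "Patients in the control group were not given any" added treatment, so there is no product for controls to stop.
- **Stopping (Trial participants).** "Participants taking probiotics were instructed to discontinue probiotic intake if they experienced any serious adverse events requiring intervention". The protocol does not say whether these patients are still sampled or analysed.
- **Blinding (Trial participants).** There was no placebo: "no identical-appearing placebo powder could be obtained".
- **Follow-up.** Trial design describes "one follow-up visit during a 60-days supplementation period". Biochemical measurements says "Fasting blood samples were collected from the participants at baseline and week 12". A patient who misses the follow-up visit therefore has no post-baseline marker value, and the two sections disagree on the length of the period.

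**The concern.** The completer rule can be read in two ways.

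1. Completed means attended follow-up and was sampled. This is the more natural reading, because the rule covers both arms and controls took no product. Only patients without a follow-up sample are then left out.
2. Completed means finished the supplementation. Probiotic patients who stopped are then removed even if they were sampled, and no matching rule applies to controls.

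The SAP does not settle which applies, so two analysts could build different datasets from it. Under either reading, no planned analysis shows whether the conclusion depends on the patients left out.

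Patients know their arm, so who attends, and why others do not, may differ between arms. If the patients lost differ from those kept in hs-CRP, ceruloplasmin, MDA or GSH, and the pattern differs by arm, the group comparison is biased. The bias could favour either arm.

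**Working it through.** **No plan figure to reproduce.** The documents give no loss rate and no dropout allowance. The sample-size statement is: "Power analysis was performed and the sample size was calculated as 79 with a statistical power of 80% and an effect size of 0.35". The step from 79 to 80 only equalises the groups. The check below does not depend on the 79.

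**Inputs from the documents.** 80 patients allocated alternately, so 40 per arm (protocol, Trial participants); 5% significance level and an independent-groups t test (SAP).

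**Assumptions.** Two-sided test (the SAP does not state sidedness); one marker with SD 1 on the analysis scale; no true effect. In an arm of 40, k patients are lost, and they average δ SD worse than those kept. Worse means higher hs-CRP, ceruloplasmin or MDA, or lower GSH. Every k and δ is assumed.

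**Formulas.** If all 40 average 0 and the k lost are δ worse than the 40 − k kept, those kept look better by kδ/40. With subscripts P (probiotic) and C (control):

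- false shift = (k_P δ_P − k_C δ_C)/40
- standard error = √[1/(40 − k_P) + 1/(40 − k_C)]
- noncentrality = false shift / standard error
- false-positive rate = probability that a noncentral t with 78 − k_P − k_C degrees of freedom exceeds the two-sided 5% limit

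**Same δ in both arms:**

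| Lost: probiotic, control | Shift at δ = 0.5 | Rate | Shift at δ = 1 | Rate |
|---|---|---|---|---|
| 1, 0 | 0.0125 | 5.0% | 0.025 | 5.1% |
| 2, 0 | 0.025 | 5.1% | 0.05 | 5.5% |
| 4, 0 | 0.05 | 5.5% | 0.10 | 7.1% |
| 8, 0 | 0.10 | 7.0% | 0.20 | 13.2% |
| 4, 2 | 0.025 | 5.1% | 0.05 | 5.5% |
| 8, 4 | 0.05 | 5.5% | 0.10 | 6.9% |
| 4, 4 | 0 | 5.0% | 0 | 5.0% |

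Worked line for (8, 0) at δ = 1: shift = 8/40 × 1 = 0.20; standard error = √(1/32 + 1/40) = 0.237; noncentrality = 0.20/0.237 = 0.84; with 70 degrees of freedom the rate is 13.2%. Reversing the losses, for example (2, 4) instead of (4, 2), gives the same rate with the bias against the probiotic.

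**Equal numbers lost for different reasons.** Take (4, 4) with δ_P = 1 and δ_C = 0. The shift is 4/40 × 1 = 0.10; the standard error is √(2/36) = 0.236; the noncentrality is 0.10/0.236 = 0.42; the rate is 7.0%. Equal counts therefore do not rule out bias. What removes it is equal counts with the same gap in both arms.

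**The case against.** **No group comparison as allocated.** A reader might infer that the SAP plans none. The documents do not support that. The protocol labels the groups by allocation, the SAP lists independent-group tests, and nothing suggests regrouping by product taken. What is missing is an explicit statement that sampled patients who stopped the product are retained.

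**Exclusion after serious adverse events.** A reader might also infer that such patients were dropped. The documents do not say that any patient stopped, or that any was excluded. On the more natural reading, stopping excludes nobody, and the replacement sentence below leaves the dataset unchanged. That part of the objection stands. The wording still permits the other reading, and the missing sensitivity analysis matters under both.

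**Size.** Most of the assumed cases stay at or below 5.5%; only large, selective loss from one arm passes 10%. This also stands. A much larger distortion can be produced: losing exactly the worst 20% of probiotic-arm values gives a false shift of 0.35 SD and a rate of about 39%. That is an extreme bound, and nothing in the documents makes it likely.

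**Value of analysing as allocated.** Allocation was alternate, so analysis as allocated preserves no randomisation. That is true. It still prevents exclusions made after allocation from changing the two groups in different ways.

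**Conclusion.** The point holds as a minor one. The stated analysis set is completers, the term is open to two readings, and no planned analysis tests dependence on missing follow-up. Bias can arise from losses that differ by arm in number or in reason, and it can run in either direction. Its actual size and direction cannot be determined, because the documents report no losses. Under the assumptions above the false-positive rate stays near 5% for small or balanced, similar losses, is about 7% with 4 of 40 selective losses in the probiotic arm (with or without 4 typical control losses), and is about 13% with 8 of 40 in one arm only. If every allocated patient was sampled and none was excluded, the completer and allocated sets coincide and there is no bias from this source.

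**What to change.** Replace the SAP sentence with: *Every patient with a follow-up sample is analysed in the group to which they were allocated, whether or not they continued the probiotic.*

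Then:

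- **Main comparison.** Compare the follow-up marker between arms adjusted for its baseline value, on the log scale for skewed markers such as hs-CRP. Baseline is already collected. The adjustment adds precision and protects against baseline imbalance; it does not repair selective loss.
- **Losses.** Report the number and reasons for missing follow-up by arm. If there were none, saying so settles the question.
- **Sensitivity analysis, only if values are missing.** Impute the missing follow-up values in all allocated patients, by arm, from the baseline marker. Shift the imputed values in either arm and in both directions over a stated range, and say whether the conclusion changes. Shifts of 0.5 and 1.0 SD are an example and an assumption; the documents give no basis for a range.
- **Completion of supplementation.** Any analysis limited to patients who finished the product is secondary. The 60-day and 12-week statements must be reconciled before it can be defined.

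**Cost.** No added visit. The main cost is SAP wording and one conditional analysis. Shifting one arm at a time with the example range gives 2 arms × 2 directions × 2 sizes = 8 results per marker, or 32 for the four primary markers, from one repeated procedure. If patients who stopped had been excluded, including them may slightly dilute the estimate. Both documents are written in the past tense; if sampling is over, the revision is limited to samples already taken and must be labelled post hoc.

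### The SAP picks each test from a normality pre-test, plans no between-arm effect or confidence interval, and leaves the baseline value unused as a covariate; the last, with the choice of scale, is what costs power

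*SAP*

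**What the plan says.** The whole analysis plan is one paragraph of the SAP. On choosing a test it says "Kolmogorov-Smirnov normality tests were used to determine whether the data showed normal distribution". Data judged normal go to t tests, for independent or for paired groups. For data judged otherwise, the SAP turns to ranks: "non-parametric tests (Mann-Whitney U test, Wilcoxon Signed Rank Test) were used in the analysis of non-normally distributed data". For description, "continuous variables were presented as mean, standard deviation, minimum value and maximum value". The threshold is given as "Statistical significance level was accepted as $p<0.05".

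The SAP does not state:
- which data the normality test is applied to (baseline, follow-up or change; each arm or pooled) or at what level;
- what happens when those verdicts conflict;
- whether the between-arm test uses follow-up values or changes from baseline;
- any between-arm difference, confidence interval, median, transformation or baseline-adjusted model.

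The Protocol has no analysis text that fills these gaps. Its Trial design section makes hs-CRP, Cp, MDA and GSH primary, the first two in the words "specifically focusing on a significant decrease in hsCRP and Cp levels". Its Biochemical measurements section has blood taken at baseline and at week 12, so a baseline value of each marker exists.

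**The concern.** There are three separate problems.

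1. The quantity compared is not fixed in advance. A t test compares means and a Mann-Whitney test compares ranks. Which of them judges a primary marker depends on the trial's own data, and whether it is applied to follow-up or to change is left open.
2. Nothing is estimated between arms. The aim is to learn what the probiotic does to each marker, yet the planned output is a p-value and a description of each group. If the rank test is chosen, the mean and SD beside it are not what was tested.
3. The baseline value is collected but not used to reduce residual variation. With about 40 patients per arm this matters for power.

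**Working it through.** **Inputs from the documents.** The Protocol (Trial participants) plans 80 patients in two groups, so 80/2 = 40 per arm. The significance level is 0.05; sidedness is not stated and two-sided is assumed.

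**The plan's own figure.** The Protocol says "the sample size was calculated as 79 with a statistical power of 80% and an effect size of 0.35". Read as a standardised difference between two means, n per arm = 2(1.96 + 0.842)²/0.35² = 15.70/0.1225 = 128.2, so 129 per arm and not 79 in total. The Protocol does not say what 0.35 measures. This is a separate matter, and nothing below depends on it except the 40 per arm.

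**Assumptions, none given in the documents.** Markers are lognormal. The baseline to follow-up correlation is ρ, on the log scale. The Kolmogorov-Smirnov test is run in each arm at 0.05, using the Lilliefors correction unless stated otherwise. The SAP route is then a t test or a Mann-Whitney test.

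**Step 1. Does the pre-test cost power?** Simulation, 3,000 trials per row, follow-up values, effect 0.35 log-SD, ρ = 0.6:

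| log-SD | always t | always Mann-Whitney | SAP route | log ANCOVA | SAP route, no effect |
|---|---|---|---|---|---|
| 0.01 (near-normal) | 0.350 | 0.332 | 0.348 | 0.508 | 0.049 |
| 0.3 | 0.332 | 0.321 | 0.337 | 0.474 | 0.057 |
| 0.5 | 0.317 | 0.328 | 0.335 | 0.482 | 0.052 |
| 1.0 | 0.226 | 0.316 | 0.316 | 0.475 | 0.047 |

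The SAP route matches the better of the two tests in every row. Type I error, on follow-up or change, ran from 0.043 to 0.057. On change scores the SAP route had power 0.424, 0.362, 0.331 and 0.289, again below log ANCOVA.

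**Step 2. What does baseline adjustment give?** For normal data on the analysis scale, ANCOVA power = Φ(d/√(1 − ρ²) × √(n/2) − 1.96), with n = 40 and √20 = 4.472.
- d = 0.35, unadjusted: Φ(1.565 − 1.96) = 0.35.
- d = 0.35, ρ = 0.6: Φ(0.4375 × 4.472 − 1.96) = 0.50. Over ρ = 0.3 to 0.8 the power is 0.375 to 0.742.
- d = 0.5, unadjusted: Φ(2.236 − 1.96) = 0.61.
- d = 0.5, ρ = 0.5: Φ(2.582 − 1.96) = 0.73.
- d = 0.5, ρ = 0.7: Φ(3.131 − 1.96) = 0.88.

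**Step 3. The planned route against ANCOVA.** Simulation, effect 0.5 log-SD, log-SD 0.3 to 0.5, ρ = 0.5 to 0.7:

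| Analysis | Power |
|---|---|
| SAP route on change | 48-75% |
| SAP route on follow-up values | 57-59% |
| Raw-scale ANCOVA | 66-85% |
| Log-scale ANCOVA | 70-87% |

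**Step 4. Separating scale from adjustment.** At log-SD 1.0 and ρ = 0.7, on change: SAP route 62%, always Mann-Whitney 62%, always t 41%, t test on log change 82%, log ANCOVA 87%, raw-scale ANCOVA 60%. Of the 25 points between 62% and 87%, 20 come from the log scale and 5 from adjustment.

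**Step 5. How often do the normality verdicts conflict?** Share of simulated trials in which the four arm-by-visit sets of one marker do not all get the same verdict:

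| Version of the test | log-SD 0.3-0.5 | log-SD 0.8-1.0 |
|---|---|---|
| Lilliefors-corrected (cut-off 0.139) | 69-83% | 7-29% |
| Uncorrected (cut-off 0.210) | 3-24% | 77-82% |

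**The case against.** The strongest defence is that the two-step rule does no statistical harm. It holds Type I error near 5% and keeps the power of the better test; for heavily skewed data it clearly beats always using the t test. All of that stands. A reader might infer that the pre-test, or the absence of an effect estimate, is what loses power. Step 1 shows otherwise for the pre-test, and leaving out an estimate cannot change the power of a test.

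A second objection is that log-scale ANCOVA does well partly because the data were simulated from that model. This stands in part. At log-SD 1.0, raw-scale ANCOVA (60%) is no better than the SAP route on change (62%), so adjustment alone is not a cure for strong skewness. At log-SD 0.3 to 0.5, raw-scale ANCOVA still reaches 66-85%.

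Third, a reader might infer that conflicting normality verdicts are the norm. They range from about 3% to 83%, depending on skewness and on the version of the test, and the SAP names no version. For the between-arm test alone, the two arms disagree at follow-up in at most 49% of trials. Likewise, the t and Mann-Whitney tests on change fall on opposite sides of 0.05 in 7-27% of trials. That is not an error rate, since only one of them is reported for each comparison.

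None of this answers the silence on what is compared or the missing estimate and interval.

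**Conclusion.** The point holds in this form. The SAP lets the data choose the test, leaves open whether follow-up or change is compared, and plans no between-arm effect or interval. A rank p-value may be paired with a summary that it does not test. These are facts of the text and need no assumptions.

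The power loss is real but comes from not using baseline as a covariate and from the choice of scale. Its size is conditional. For an effect of 0.5 log-SD, log-SD 0.3 to 0.5 and correlation 0.5 to 0.7, it is the gap between 48-75% (change) or 57-59% (follow-up) and 70-87%. At log-SD 1.0 most of the gain over the change-score route comes from the log scale. The documents give no SD, distribution or correlation for any marker, so these ranges illustrate the loss and do not forecast it.

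The documents do not support a claim of inflated Type I error, or a case for log-transforming every marker. The matter should be corrected, but it does not by itself invalidate the planned tests.

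**What to change.** Remove the normality test as the rule for choosing a test. Replace it with wording such as:

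*For each primary and secondary continuous outcome, the week-12 value is compared between arms by ANCOVA with the baseline value of that outcome as covariate, reported as an adjusted difference with 95% CI. Markers named in advance as right-skewed (for example hs-CRP and TG) are analysed on the log scale and reported as a ratio of geometric means with 95% CI. A rank-based ANCOVA is a sensitivity analysis. Skewed markers are summarised by median and quartiles.*

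The Protocol's Trial design section describes the trial as already conducted, between July 2020 and June 2023. If the data have been analysed, this analysis should be labelled as added after the plan and reported beside the planned tests, not in place of them. The same section gives a 60-day supplementation period while later sections give 12 weeks; these must be reconciled so that the analysed time point is unambiguous.

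Cost: wording, and one standard model in the software that the SAP names. No new data are needed. Log-scale results read as ratios instead of differences, and the gain in power depends on a correlation and a distribution that the documents do not give.

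### The plan does not say which test decides the primary outcomes, so a before–after test in the probiotic arm alone could meet one; no baseline-adjusted between-arm comparison is specified

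*SAP*

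**What the plan says.** The protocol (Methods, Trial design) describes a controlled study and defines the primary outcomes as "the effects of the intervention on inflammatory markers, specifically focusing on a significant decrease in hsCRP and Cp levels", and for oxidative stress as "including a significant reduction in MDA levels and a significant increase in reduced GSH levels". It does not say what the decrease or increase is measured against.

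The SAP is one paragraph. For normal data: "Parametric tests (t test in independent groups, t test in dependent groups) were used in the analysis of normally distributed data". For other data: "non-parametric tests (Mann-Whitney U test, Wilcoxon Signed Rank Test) were used in the analysis of non-normally distributed data". Each pair contains one between-arm and one within-arm test. Normality decides parametric or non-parametric; nothing decides between-arm or within-arm. The SAP does not say whether follow-up values or changes are compared, and it names no ANCOVA, regression or other adjusted model.

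Three other statements bear on the point:
- Biochemical measurements: "Fasting blood samples were collected from the participants at baseline and week 12", so a baseline value should exist for each primary marker.
- Trial participants: "Dietary habits, physical activity, and glucose-lowering therapy of the participants were not intervened during the study".
- Trial participants, on assignment to arms: "Participants were allocated sequentially according to order of presentation (alternate allocation". The control arm received no placebo.

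**The concern.** Two separate things are at stake.

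1. **Validity.** A paired test in one arm asks whether that arm changed, not whether the probiotic changed it. Seasonal effects, regression to the mean, altered medication or behaviour, or assay drift move both arms and would be credited to the probiotic. Because diet, activity and glucose-lowering therapy were left to run their course, shared change cannot be excluded. The control arm exists to remove it, and a within-arm test sets that arm aside. The listed between-arm tests do not have this fault, but nothing makes them decisive.

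2. **Efficiency and choice of variable.** A between-arm test on follow-up values ignores the baseline; one on changes uses it less efficiently than ANCOVA. Which of the two is stronger depends on the baseline to follow-up correlation, so leaving the variable open also leaves room to choose after seeing the data.

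**Working it through.** **Inputs.** From the documents: 80 patients planned in two groups, taken as 40 analysed per arm; significance at p<0.05; and "the sample size was calculated as 79 with a statistical power of 80% and an effect size of 0.35". Assumed, because the documents do not give them: two-sided testing, normal data with equal SDs, no dropout, the size of any shared change, and the baseline to follow-up correlation r.

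**The plan's own figure.** The 79 is not reproduced by any between-arm test of a continuous marker that was tried. With 0.35 as a standardised mean difference d, a two-sided two-sample t test needs 130 per arm (260 in all). With 0.35 as Cohen's f for two groups, 67 in all. A paired t test needs 67. A chi-square test with w = 0.35 and 2 df gives 79, but it is not a test of a continuous marker. As neither the test nor the type of effect size is stated, both readings (d = 0.35; f = 0.35, so d = 0.7) are carried forward. The sample-size figure therefore does not show which test was meant to decide.

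**Step 1: false positives under shared change.** Suppose the probiotic does nothing and both arms improve by dz SDs of change. The paired t test in one arm has 39 df and noncentrality dz × √40; at dz = 0.3 this is 0.3 × 6.325 = 1.90. The third column is the second multiplied by the chance that the control arm's test is non-significant; at dz = 0.3, 0.456 × 0.544 = 0.248.

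| Shared drift dz | Probiotic arm significant, favourable | Probiotic significant, control not |
|---|---|---|
| 0.1 | 9% | 8% |
| 0.2 | 23% | 18% |
| 0.3 | 46% | 25% |
| 0.5 | 87% | 11% |
| 0.7 | 99% | 1% |

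The third column has the form p(1 − p), so about 25% is its ceiling when drift and arm size are equal. In simulation (20,000 runs, r = 0.6) the between-arm tests rejected in 4.8% to 5.3% of trials at every drift, both directions counted. The like-for-like figure, favourable direction only, is about 2.5%.

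Drift here is in SDs of change. One SD of change equals √(2(1 − r)) SDs of the raw marker: 1.18, 0.89 and 0.63 at r = 0.3, 0.6 and 0.8. A drift of 0.5 is thus 0.59, 0.45 or 0.32 raw SD.

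**Step 2: power of the between-arm options.** Two-sample noncentral t with noncentrality δ × √(40/2), where δ = d for follow-up values, d/√(2(1 − r)) for change, and d/√(1 − r²) for ANCOVA (77 df; 78 for the others). Example, d = 0.35 and r = 0.6: δ = 0.35, 0.391 and 0.437.

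| Reading of 0.35 | r | Follow-up t | Change t | ANCOVA | Gain over best listed t test (points) |
|---|---|---|---|---|---|
| d = 0.35 | 0.3 | 34.0% | 25.7% | 36.7% | 2.7 |
| d = 0.35 | 0.6 | 34.0% | 40.9% | 48.9% | 8.0 |
| d = 0.35 | 0.8 | 34.0% | 68.6% | 73.1% | 4.5 |
| d = 0.7 | 0.3 | 87.1% | 74.3% | 90.0% | 2.9 |
| d = 0.7 | 0.6 | 87.1% | 93.3% | 97.2% | 3.9 |
| d = 0.7 | 0.8 | 87.1% | 99.8% | 99.9% | 0.1 |

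The follow-up test beats the change test at r = 0.3 and loses to it at 0.6 and 0.8; ANCOVA is the best of the three throughout.

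**Step 3: does the choice of adjustment move the estimate?** With equal SDs, the ANCOVA and change-score estimates differ by (1 − r) times the baseline difference between arms. For a baseline difference of one standard error, √(2/40) = 0.22 SD, that is 0.16, 0.09 and 0.04 SD at r = 0.3, 0.6 and 0.8.

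**The case against.** The natural reading of a controlled study that reports intervention effects, has an untreated control group and lists between-arm tests is probiotic versus control, with paired tests as description. The documents nowhere say that a paired test decides efficacy. That is fair, and the point claims only that the text permits it. But the outcomes are worded as a significant decrease or increase, which is what a paired test reports, and no other section closes the gap.

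The drift is assumed. No section gives a shared change, and leaving diet and therapy alone is not evidence that they changed; the protocol also includes diet and activity questionnaires. This stands as a limit: the first table is a conditional illustration, not an estimate for this trial.

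A t test on change is a valid between-arm analysis, and ANCOVA's advantage over the better listed t test is modest. This also stands. The adjustment is a low-cost improvement; the unspecified contrast is the more serious fault.

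Under open alternation, equal expected baselines are not guaranteed, and the documents cannot settle whether ANCOVA or change is less biased. This is why both should be reported. Naming either in advance would cure the ambiguity.

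**Conclusion.** The concern holds and should be fixed. The text leaves open whether a between-arm or within-arm test decides each of the four primary outcomes, and on which variable. If a paired test is used, its false-positive rate depends on shared change: 9% at 0.1 SD of change to 99% at 0.7, against about 2.5% in the same direction for a between-arm test. If a between-arm test is used, there is no such inflation, and the loss is the smaller one of not using the baseline fully: 0.1 to 8 percentage points of power. If 0.35 is a standardised mean difference, ANCOVA with 40 per arm still falls short of 80% at the correlations shown, so adjustment does not repair the sample size.

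The wording gap rests on the text alone. The sizes rest on the assumptions listed in the working. Combining four primary outcomes is a separate matter.

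**What to change.** - **Protocol, Trial design:** word each primary outcome as the difference between arms (probiotic minus control) at follow-up, adjusted for baseline. The follow-up time must be reconciled first: this section gives 60 days, while the intervention and biochemical sections give 12 weeks.
- **SAP, primary test:** for each marker, an ANCOVA of the follow-up value on arm and baseline value, reported as an adjusted difference with a 95% confidence interval. For skewed markers such as hs-CRP, analyse on the log scale and report a ratio of geometric means.
- **SAP, within-arm tests:** keep them as description, and rest no efficacy claim on them or on one arm being significant and the other not.
- **SAP, sensitivity:** also report the between-arm comparison of changes. State that ANCOVA adjusts for observed imbalance in the baseline marker but does not remove selection bias from open alternation.
- **Disclosure:** the SAP is written in the past tense. If the data have been analysed, present this as a revised analysis.

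The cost is wording in two places, a few lines of SPSS syntax and one degree of freedom per model. No new data are needed. If results exist, a disclosed reanalysis is required.
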